1. For single-site studies - CMCVAMC is the only institution involved. Yes No
2. For multi-center studies.
 - 2.1. CMCVAMC is the Coordinating Center in which the PI is the lead investigator. Yes No N/A
 - 2.2. Provide the name of the Coordinating Center. Yes No N/A
 - 2.3. List the name of the other sites involved.
 - 2.4. Provide the FWA numbers for each of the other sites involved.

THE FOLLOWING INFORMATION MUST BE CMCVAMC-SPECIFIC, THAT IS, SPECIFIC TO WHAT WILL BE DONE WITH CMCVAMC-RECRUITED VETERANS.

H. Background and Significance: (Describe succinctly and clearly the past findings which justify the plan for this project. A summary of the relevant literature in the area of interest and reports of previous studies should be included.)

Peer support and particularly mentors have been shown to help African American diabetic veterans with poor diabetes control improve their glucose control. Ongoing studies are testing whether mentors can help non-veterans and populations including a larger sample size of women. Peer mentors may be particularly effective in a VA setting where many patients lack social support and a culture of camaraderie is strong. However, it is unknown if improvements persist once mentoring stops, how to best sustain such programs and whether peer support models would be effective in veterans from all ethnic racial groups.

Purpose of the Project: (Clearly provide the purpose of this research project.)

In this study, we propose a randomized controlled trial of poorly controlled diabetic veterans in which poorly controlled veterans of all race/ethnicities first enroll as mentees in a program for diabetic veterans and then as mentors to test a model of sustainability. In addition, given a growing literature that being a mentor is good for your health besides from creating sustainability for the program it may help sustain

effects. This study will have 4 arms: 1. Usual care (enrolled at two different time points); 2. Peer mentoring where mentors are veterans who were once in poor control but are now in good control; 3. Peer mentoring where the mentoring comes from former mentees from arm 2 (mentoring FFM); and 4. Former mentees from arm 2 not randomized to becoming a mentor. Ultimately we aim to create programs that can serve to sustainably support VA Patient Aligned Care Team (PACT) efforts.

Describe the Research Questions or Hypotheses (that is, what questions are you trying to address by conducting the research.)

Our primary aims are as follows.

1. Test the effectiveness of a peer mentor model in a mixed race population of poorly controlled diabetic veterans.
H1: Compared to usual care, veterans in the peer mentor arms will have improved hemoglobin (HbA_{1c}), blood pressure, LDL levels, DM quality of life, and depression scores regardless of race or ethnicity at the end of the intervention (tested at 6 months) and effects will persist (tested at 12 and 18 months).
2. Test the effectiveness of using former peer mentees as peer mentors.
H2: Compared to usual care, veteran who receive peer mentoring from former mentees will have improved hemoglobin (HbA_{1c}), blood pressure, LDL levels, DM quality of life, and depression scores at the end of the intervention (tested at 6 months) and effects will persist (tested at 12 and 18 months).
3. Assess the effects of becoming a mentor on those who were originally mentees.
H3: Compared to past mentees who are not randomized to becoming a mentor, past mentees randomized to becoming a mentor will have better glucose control, blood pressure, LDL levels, DM quality of life, and depression scores.
4. Conduct a rigorous qualitative evaluation examining in-depth the mentor-mentee relationship, the transition to becoming a mentor, qualities of a successful mentor, and factors relevant to broader program implementation.

Secondary Aims:

5. In those randomized to being a mentee, explore mentor characteristics associated with improved HbA_{1c}. Predictors to be evaluated include past mentoring dose of the current mentor, the mentor's past change in HbA_{1c}, the mentor's starting HbA_{1c}, current mentoring dose provided by the mentor, mentee's evaluation of the mentor, and mentor's depression score at baseline.

- I. **Primary Outcome Variable(s):** (Define the primary outcome variable(s) used to support the study objectives (e.g. if the objective is to show that treatment A is superior to treatment B in the treatment of subjects with essential hypertension, the primary outcome variable is blood pressure measurement.)

The primary outcome variable will be change in glucose control as measured by the HbA_{1c} assessed at baseline, 6 months, 12 months and 18 months.

- J. **Secondary Outcome Variable(s):** (Define the secondary outcome variables. Such measured variables should also include the timing of measurement.)

Secondary outcome variables will include blood pressure, serum LDL, diabetes quality of life measured by the self reported Diabetes Distress Scale, and depression assessed with the PRIME-MD Patient Health Questionnaire (PHQ-9). All secondary outcomes will also be measured at baseline, 6 months and 12 months.

K. Study Design and Methods:

1. Is this a clinical trial? YES NO
 1.1. If yes, what type? Check all that apply.
 Phase I Phase II Phase III Phase IV
 1.2. If yes, this study must be registered on Clinicaltrials.gov.

2. Design

2.1. What research methods will be used in the project? Check all that apply.

 Surveys/Questionnaires	 Interviews	 Audio Taping
 Behavioral Observations	 Chart Reviews	 Video Taping
 Focus Groups	 Randomization	 Double-Blind
 Control Group	 Placebo	 Withhold/Delay Treatment
 Specimen Collection	 Deception	 Telephone Survey
 Other (Describe)		

[figure not shown]
2.2. Describe how randomization or other treatment assignment will be made.

After informed consent is obtained and the baseline interview is complete, participants will be randomized. Randomization will be a staged process (see figure 1). For both steps, randomization will be conducted by the study statistician using a random number generator and via permuted block randomization with variable block size to force balance among treatment group assignments after every block of participants is enrolled.

At stage 1, interested participants will be randomized to usual care or peer mentoring. At stage 2, interested participants will be randomized to usual care or peer mentoring from a former mentee (FFM). In addition, former mentees will be randomized to either becoming a mentor or usual care (i.e. mentee assigned or no mentee assigned).

To date we have been randomizing patients in a 1:1 manner. After receiving IRB approval for this modification we will change to 2:1 randomization (2 to an intervention arm for every 1 enrolled into usual care). See below for exact numbers.

Figure 1 Randomization

2.3. For retrospective research studies, provide the “look-back” period. (e.g., December 1, 1999 through December 31, 2008.)

[figure not shown]
3. Study Duration

3.1. Provide the estimated length of time to enroll all subjects and complete the study.

We want to enroll a total of 492 poorly controlled diabetic veterans and 206 mentors with currently good glucose control. In stage 1 there will be 206 poorly controlled diabetics in the peer mentoring arm and 206 mentors. Mentors who withdraw from the study will be replaced by additional mentors to ensure that all 206 poorly controlled diabetics in the peer-mentoring arm have mentors. In stage two there will be 144 mentors (former mentees) of which 72 will be randomized to being a mentor and 72 will be randomized to usual care. In addition, there will be 128 poor controlled diabetics 56 of whom will be in usual care and 72 of whom will be randomized to receiving peer mentoring from FFM. We project being able to enroll 7-8 new poorly controlled diabetics per week with two research assistants. Even considering the staggered start times, we anticipate it will take 14-16 months to complete enrollment and another 18-24 months to complete follow-up for a total of 38-40 months. After that we anticipate it will take an additional 1-2 months to complete the analysis. See sample size section for further description of required sample.

3.2. Explain the expected duration of subject participation including any follow-up.

The active time for each participant in the study will be roughly 18-24 months depending on which arm they are randomized to. 12-18 months of face-to face visits with an additional 6 months after the last in-person visit where each participant’s electronic medical record (EMR) will be under electronic review. Figure 2 depicts the flow of participants through the study.

Figure 2: Flow of Participants Through Study

3.3. Specify the projected date of completion of the proposed study.

Enrollment started September 27, 2012 and we anticipate completion of the study by December 31, 2015

4. **Drug Information** (If not applicable state, "Not Applicable.") **N/A**

- 4.1. Specify if the drug or biological agent is:
 - 4.1.1. FDA approved
 - 4.1.2. Used for off-label purposes
 - 4.1.3. Not yet FDA approved.
- 4.2. Include the FDA Investigational New Drug (IND) number for all non-FDA approved and off-label drugs, biological agents or nutritional supplements. If not applicable state, "Not Applicable."
- 4.3. Provide all relevant information about the drug
- 4.4. Explain any wash-out periods, rescue medications permitted and any type of medications not permitted while enrolled in the study.
- 4.5. Describe blinding and un-blinding procedures.
- 4.6. Include the dosage, route of administration, previous use, and the safety and efficacy information on any drug used for research purposes.
- 4.7. Describe rationale for the dosage in this study.
- 4.8. Justify why the risks are reasonable in relation to anticipated benefits and/or knowledge.
- 4.9. Describe where drug preparation will be done.
- 4.10. All drugs for CMCVAMC subjects must be dispensed through the VA investigational pharmacy.
- 4.11. Describe where the study treatment will be administered.

- 4.12. Describe plan for tracking a non-compliant treatment study subject.
- 4.13. Summarize any pre-clinical data.
- 4.14. Describe the process for the storage, security, dispensing and return of an investigational drug.

5. **Investigational Device** (If not applicable state, "Not Applicable.") **N/A**

- 5.1. The Investigational Device Exemption (IDE) number must be submitted for all significant risk devices and if an IDE exists for a non-significant device.
- 5.2. Significant Risk or Non-significant Risk - If a device is not approved by the FDA, specify whether or not the sponsor has determined this device to be a "significant risk" or "non-significant risk" as defined by the FDA.
- 5.3. Provide all relevant information about the device.
- 5.4. Describe blinding and un-blinding procedures.
- 5.5. Specify if device is:
 - 5.5.1. FDA approved
 - 5.5.2. Used for off-label purposes
 - 5.5.3. Not yet FDA approved.
- 5.6. Explain if the investigational device will be delivered and/or stored by the Principal Investigator or Pharmacy Services.
- 5.7. Describe the process for the storage, security, dispensing and return of an investigational device.
- 5.8. For research involving an investigational device, describe the SOP or plan for device control.
- 5.9. Address how the device will be stored in such a way that only research staff associated with the protocol will have access to the device.
- 5.10. Describe measures that will be put into place to ensure that the device will only be used in participants of this research protocol.

L. **Does this project involve international research?** YES NO

- 1. For further instructions refer to VHA Directive 2005-050, *Requirements for Conducting VA-Approved International Research Involving Human Subjects, Human Biological Specimens, or Human Data*
- 2. *VHA Handbook 1200.05 definition of international research - VA international research is any VA-approved research conducted at international sites (not within the United States (U.S.), its territories, or Commonwealths); any VA-approved research using either human biological specimens (identified, de-identified, or coded) or human data (identified, de-identified, or coded) originating from international sites; or any VA-approved research sending such specimens or data out of the U.S. (see par. 56). NOTE: For the purposes of this Handbook, research conducted at U.S. military bases, ships, or embassies is not considered international research.*

M. **Study Procedure**

1. **Study Procedures**

- 1.1. Outline all study procedures - (*If necessary, include a table or flow chart, showing the schedule of the procedures and interactions. Distinguish between interventions that are experimental and carried out for research purposes vs. those that are considered standard of care. Routine procedures that are performed solely for research purposes should also be identified.*)

Overview: We will perform a randomized controlled trial with four arms. The aim is to create a program that can augment PACT efforts.

Patients and Settings: We will enroll veterans with diabetes mellitus (DM) who receive their care from the CMC VA Medical Center (CMCVAMC). Veterans between the ages of 30 and 75 years of age -- patients most likely to reap the benefits of gaining control -- will be eligible for participation. There will be 4 arms: 1. Usual care (enrolled at two different time points); 2. Peer mentoring where mentors are veterans who were once in poor control but are now in good control; 3. Peer mentoring where the mentoring comes from former mentees from arm 2 (mentoring FFM); and 4. Former mentees from arm 2 not randomized to becoming a mentor. To ensure that we are targeting those most likely to benefit from improving control we enroll diabetics with persistently poor DM control. Persistently poor DM control will be defined as having an HbA1c > 8% on 2 different occasions in the course of 24 months, with at least 1 measure within 3 months of enrollment. Mentors for arm 2 will have previously been in poor control and are now in good control, defined as having an HbA1c of > 8% in the past 3 years and an HbA1c \leq 7.5% within 3 months of enrollment. They will also, when feasible, be the same race, sex, and age (\pm 10 years) as their mentee. When possible, if the mentee is on insulin we will seek out a mentor on insulin. These criteria for selecting both mentees and mentors have led to successful mentoring partnerships in our prior work. Patients will be identified by the Center for Evaluation of PACT (CEPACT) through VISN 4 Data Warehouse (VDW). With IRB approval, CEPACT will extract administrative, clinical, and laboratory data from the VDW on an ongoing basis. The VDW is updated regularly and thus an excellent source of up-to-date patient information. Identified patients will be sent a letter describing the study and then called. The PI has used this method to identify veterans with DM on many occasions and routinely is able enroll between 60-70% of those contacted. Potential mentors for arm 2 will be identified and approached in a similar manner. Veterans who agree to participate will be invited into the CMC VAMC to complete a consent procedure, baseline survey, and have their blood drawn to determine their HbA1c at enrollment. All enrollees and mentors will receive, regardless of the arm, \$50.00 for each visit requiring a blood draw and survey completion (baseline, 6 months, 12 months, and depending on arm, potentially 18 months).

At the end of 6 months, those randomized to receiving a mentor in stage 1 will be re-randomized to either becoming a mentor (arm 2) or not becoming a mentor (arm 4). Those who do not become a mentor will continue to be followed. Those randomized to being a mentor will become mentors for arm 3 participants. For arm 3, matching will be tailored to the best of our ability since the pool of mentors will be limited to those who were previously mentees. We have built in over-enrollment into stage 1 to allow for some loss to follow-up and selective removal of participants who might be inappropriate mentors. Potential mentees for stage 2 will be identified and contacted in the same manner as those identified for stage 1. Those interested in participating will be randomized to usual care or mentoring from FFM. As with stage 1, participants will receive \$50 to reimburse them for their time for all required in person visits.

Procedures: As mentioned there will be 4 arms. Randomization into each arm is described above.

Arm 1 Usual Care: They will complete all planned surveys, interviews and blood draws (baseline, 6 months, 12 months). In addition, all participants' medical health record will be under electronic review for an additional 6 months after their last visit. They will be notified of their starting HbA1c and the American Diabetes Association (ADA) and VA recommended goals for HbA1c. No additional interventions will be provided. All participants will be called at one month and three months to check in and assess for hypoglycemic events (based on our past previous work we anticipate that these events will be rare and not differ by arm).

Arm 2 Peer Mentoring: In addition to being notified of their starting HbA1c and ADA and VA recommendations for HbA1c, arm 2 will be told that within the next 1-3 weeks we will find them a peer mentor who will start calling them. They will be told that they are expected to talk with the mentor at least once a week for 6 months but they can talk as much as they want. We will also

explain that we will not be setting up a face-to-face introduction but that it is fine for the two of them to meet in person if they desire. Finally, participants will be reminded that in six months time they may become a mentor. We will train them to be mentors and provide them with a mentee who is in poor diabetes control.

After being randomized to the peer mentor arm we will identify potential mentors and contact people until an eligible mentor is found. Mentors will participate in an hour long one-on-one training informed by motivational interviewing techniques. All training materials have been developed and include instruction on learning the mentee's story, understanding the mentee's motivations, helping the mentee identify the differences between their behaviors and goals, and helping the mentee identify a realistic plan for goal achievement. Open ended questions are encouraged and modeled. Mentors are also taught how to follow-up and assess progress. Sample questions will be provided. However, mentors are also encouraged to draw on their own experiences. Once a month, peer mentors will be contacted to provide training reinforcement and asked about their interactions with their mentee. Peer mentors will be given the phone number of their mentee and informed that they will receive \$20 per month for speaking at least once a week. Whether they spoke will be determined by self-report.

At the end of 6 months, at the first follow-up visit mentees will be randomly assigned to become a mentor or to not become a mentor. Those selected to become a mentor will be trained how to be mentors and told that we will contact them in the next 1-3 weeks with a mentee. They will then be asked to perform all of the activities that their mentor performed for them. Like their mentors, they will also receive \$20 per month for talking at least once a week.

Arm 3 Peer Mentoring FFM: As with the other arms the participants will be notified of their starting HbA1c and ADA and VA recommendations for HbA1c. To the best of our ability, Arm 3 will be matched with a mentor race, sex, age (± 10 years), and insulin use. The mentor will come from Arm 2 and initiate phone contact.

Arm 4 Former Mentees not Randomized to Becoming a Mentor: Arm 2 participants not randomized to becoming a mentor will be followed in the same manner as arm 2 participants randomized to becoming a mentor.

Data Collection: All participants (mentors and mentees) will complete a baseline survey, a short call at 1 and 3 months, a 6 month survey, a 12 month survey, a blood draw at baseline, 6 months, and 12 months and will have their medical health record under electronic review for an additional 6 months after the last in-person visit. Those randomized to arm 2 and further randomized to arm 4 will receive additional short calls at 7 months and 9 months and have one additional in person visit with blood draw at 18 months. A sample of mentors and mentees from stage 1 and stage 2 will be asked to complete qualitative interviews baseline, 6, 12, 18 months. Table 1 identifies data to be collected at each time point and the source of the data.

Table 1: Measurement Schedule							
	Baseline	1 M	3 M	6 M	12 M	18 M	24 M
Dependent Variables							
HbA _{1c} (blood)	x			x	x	x	
Blood Pressure (in person measurement)	x			x	x	x	
Direct LDL (blood)	x			x	x	x	
DM quality of Life (self-report) - Distress	x			x	x	x	
Depression Symptoms (self-report) - Mood	x			x	x	x	
Intervening Variables of Interest							
Social Support	x			x	x	x	
Self-Efficacy (self-report)	x			x	x	x	
Perceived Benefits and Barriers (self-report)	x			x	x	x	
Self-management Behaviors (self-report)	x			x	x	x	
Past Mentoring Dose Received by Current Mentor (Past records)	x						
Mentor's past Change in HbA _{1c} (Past study records)	x						
Mentee's assessment of mentor quality (self-report)				x	x	x	
Potential Confounders							
Demographics (self-report)	x						
Attachment Style (self-report)	x						
Perceived Need for Support (self-report)	x			x	x	x	
BMI (in person measurement)	x			x	x	x	
DM Health History (self-report)	x						
General Health History (self-report)	x			x	x	x	
Potential Contamination (self-report)				x	x	x	
Hypoglycemic Symptoms (self-report)	x	x	x	x	x	x	
Qualitative Perceptions of Program (self-report)	x			x	x	x	
Medical Record Review (Electronic medical record)**						x	x
* Current Mentoring Dose Provided by Mentor will be assessed monthly. For Ease of Presentation we did not include all collection times.							
** Exact timing of EMR review depends on arm – only reviewed once either at 18 or 24 months.							

For self-reported data we will use validated survey questions developed by the PI or other researchers in the field. The research coordinator will be trained to measure BP and pulse rate at each visit using an automatic digital blood pressure monitor on the non-dominant arm after the subject has been seated for 5 minutes. An average of two measurements will be used for analyses. We will evaluate both change in systolic and diastolic BP as well as the percent of patients in each arm with ADA target BP (BP < 130/80 mmHG). Height and weight will be measured using standard procedures with a beam balance and a strain-gauge digital scale, respectively, and used to calculate body mass index (BMI).

We will conduct the qualitative interviews with the aim of understanding how, in terms of the outcome HbA_{1c}, successful mentor-mentee pairs differed from those who were not successful. Interview guides will be informed by *adult learning theory*. We will use semi-structured interviews. Open-ended questions will be followed by probes to prompt detail and ensure that a broad range of possible responses are elicited. Using constant comparison techniques, we will modify scripts in real time as new and unexpected themes emerge.

1.2. Explain if and how the follow-up of subjects will occur.

Follow-up will occur at 1 and 3 months post enrollment with a brief phone call, and at 6 months and 12 months post enrollment at the CMC VA Medical Center. Additional short calls at 7 and 9 months and an additional in person 18 month visit will also occur for those in arm 2 and 4. After follow-up in person visits are complete, all enrolled participants' medical health record will be under electronic review for an additional 6 months.

1.3. Describe where, how and who will be conducting study procedures.

Consent, study surveys and interviews, blood pressure measurements, and weight at baseline, 6 months, 12 months and when appropriate 18 months will occur at the CMC VA Medical Center and be performed by a project manager or research assistant.

One and three month hypoglycemic assessments will be assessed over the phone by a project manager or research assistant.

Evaluations of the serum HbA1c and LDL will be performed by the CMC VA Medical Center lab.

Electronic review of medical health records will occur at the CMC VA Medical Center on the VA server network.

1.4. If a survey study, specify the estimated amount of time that subjects will need to complete the questionnaires/tools.

The below table estimates the amount of time each step will require for data collection. The amount of time spent on mentoring calls is not determined by the study.

Table 2: Data Collection Step, Time to Complete and Mode of Collection		
Procedure	Estimated Time to Complete	Number of Times to Perform
Consent	30 minutes	1 (in person)
Baseline Survey	45 minutes	1 (in person)
Lab tests	10 minutes	3-4 (in person)
Hypoglycemic Symptoms	5 minutes	2 (phone call)
Follow-up Survey	30 minutes	2-3 (in person)
Qualitative Interviews	20 minutes	2-3 (in person)
Health record review	15 minutes	1 (electronically)
Mentor Training	60 minutes	1 (in person)
Reinforcement Calls	10-15 minutes	5 (phone call)
Estimated Total Active Time for Participants		
Arm 1	175 minutes (≈ 3.0 hours)	
Arm 2	385 minutes (≈ 6.5 hours)	
Arm 3	215 minutes (≈ 3.5 hours)	
Arm 4	385 minutes (≈ 6.5 hours)	
Mentors for Arm 2	325 minutes (≈ 5.5 hours)	

Based on experience, consent will take about 30 minutes and the baseline survey will take approximately 45 minutes. Follow-up visits will take about 30 minutes for survey completion and 20 minutes for the completion of qualitative interviews. The lab usually expedites tests for research and we expect patients will need to spend approximately 10 minutes getting their blood

drawn. The total time commitment for consent and data collection is estimated to be between 3 and 7 hours depending on the arm the person is in. However, given the time commitment we will reimburse participants \$50 for each in person visit to cover time and transportation costs and an additional \$40 for qualitative interviews if they agree to complete the qualitative interview portion of the study.

- 1.5. If a blood draw, specify the amount of blood to be drawn in milliliters and in teaspoonfuls or tablespoonfuls and specify how often and where the blood will be drawn.

Blood draws will occur at the CMC VAMC lab. We anticipate a maximum of 5ccs or 1 teaspoon of blood will be required for each in-person visit at baseline, 6 months, 12 months and when appropriate 18 months..

2. **Data Collection** (Include all questionnaires and survey tools with the submission.)

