In order to assure 72 in each arm for stage 2, we will need a total of 144 mentees in stage 1. Again, to protect against possible attrition, we inflate that by 16% and enroll 171 mentees in stage 1. A corresponding number of mentors (171) will be recruited for stage 1. There will be no randomization of mentors in stage 1. Since usual care for stage 1 can be combined with usual care for stage 2, there is no need for a 1:1 randomization. Initially, a 1:1 randomization was used, but after evaluation we believe we can switch to a 2:1 randomization to avoid recruiting more usual care patients than necessary. With this change we will enroll approximately 139 patients to usual care in stage 1.

The combined number of poorly controlled diabetic patients receiving usual care will be approximately 195. The number of poorly controlled diabetic patients receiving peer mentoring will be 232 (171 in stage 1 and 72 in stage 2). The number of mentors in stage 1 will be 171, and the number of mentors in stage 2 will be 72 (from among those who received mentoring in stage 1). The total number of patients in the study will be 594.

A recent analysis of clinical data from the CMC VAMC and its surrounding CBOCs indicate that in the last year there were 1,248 patients who would have qualified to be mentees and 1,810 who would have qualified to be mentors.

4.2. Define plans for data and statistical analysis, including key elements of the statistical plan, stopping rules and endpoints.

For Stage 1: We will test these primary hypotheses using an unadjusted intent-to-treat analyses, i.e., with adjustment for only baseline HbA_{1c}. The primary tests will assess the significance of the coefficients associated with the treatment assignment in a longitudinal linear model of the repeated HbA_{1c} as a function of treatment, where the active group (peer mentoring) is compared to the control group via an indicator variable. Standard t-tests will determine whether a significant difference in HbA_{1c} improvement occurred between the treatment arm compared to the control arm. To account for the fact that we are doing multiple tests, we will use the Bonferroni method and consider a treatment to be significantly different than the control if the p-value is less than $0.05/2=0.025$.

| Stage 2 Analysis:

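### The stage 1 analysis as written does not test H1's claim that mentoring works across race and ethnicity

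*Combined protocol and SAP*

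**What the plan says.** Section H (Background and Significance) reports that peer mentoring has helped African American veterans with poor control. Among several open questions it lists "whether peer support models would be effective in veterans from all ethnic racial groups". The first primary aim is to "Test the effectiveness of a peer mentor model in a mixed race population of poorly controlled diabetic veterans", and H1 beneath it predicts improvement "regardless of race or ethnicity at the end of the intervention (tested at 6 months"), with persistence at 12 and 18 months.

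The analysis that serves H1 is the stage 1 paragraph of U.4.2. It says "The primary tests will assess the significance of the coefficients associated with the treatment assignment in a longitudinal linear model", and that "the active group (peer mentoring) is compared to the control group via an indicator variable". Baseline HbA1c is the only covariate, and the significance threshold is 0.05/2 = 0.025.

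**The concern.** H1 makes two statements: mentoring works on average, and it works whatever the patient's race or ethnicity. The planned coefficient addresses the first. It averages over the racial groups enrolled and carries no information on whether they respond alike.

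Prior evidence exists for one group, so this matters more than usual. If the benefit is again confined to that group, or to any other large one, the overall test can still succeed. H1 would then be reported as confirmed in full, although the race clause had not been examined and might be false. A reader deciding whether to offer the programme to all veterans would rely on a statement that the trial never checked.

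**Working it through.** **1. Does the plan address race anywhere else?**

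- U.4.2, H2 and H3: the interactions are between follow-up visit and intervention group. None involves race.
- U.4.2, under H2: characteristics that differ between arms at the 0.20 level enter as fixed-effect adjustments. That removes imbalance but does not let the treatment effect vary.
- U.4.2 mentions stratified randomization without naming a factor. K.2.2 describes permuted blocks only.
- U.4.2, H4: the listed predictors are mentor dose, HbA1c history, evaluation and depression. Race is not among them.
- M.1.1: race is used to match mentors to mentees. Table 1 lists self-reported baseline demographics. V.4 lists sex and race among record items.

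Race is thus used and recorded, but no analysis by race is specified.

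**2. Inputs**

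- From U.4.1: SD 1.6, design effect 0.8, 80% power, 64 per arm, 10% attrition allowance (16% for stage 1 mentees), and stage 1 sizes of 171 mentored and about 139 usual care.
- From K.3.1: 206 mentored, and by subtraction 492 − 206 − 128 = 158 usual care. The two sections disagree, so both pairs are used.
- Assumed, because the documents give no figure: two groups, a minority share f of 20 to 50%, equal in both arms.
- All power figures below are two-sided normal approximations.

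**3. The plan's own figure**

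n = 2 × (1.96 + 0.842)² × (1.6/0.8)² = 62.8, or 63 per arm; the t-test version gives 64. Then 64/0.9 = 71.1, or 72. Both figures reproduce. They size an overall comparison only.

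**4. Can the overall test succeed when the race clause is false?**

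With 171 v 139, SE = 1.6 × √(1/171 + 1/139) = 0.183. Suppose the effect is 0.8 in the majority and zero in the minority.

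| Minority share | Average effect | Average/SE | Power at 0.05 | Power at 0.025 |
|---|---|---|---|---|
| 30% | 0.7 × 0.8 = 0.56 | 3.07 | 87% | 80% |
| 20% | 0.8 × 0.8 = 0.64 | 3.50 | 94% | 90% |

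So yes, with high probability.

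**5. What would a treatment-by-race estimate deliver?**

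SE(difference) = 1.6 × √(1/n1 + 1/n0) / √(f(1 − f)). The half-width is 1.96 × SE, and power is for a true difference of 0.8 at 0.05. For 16% loss, SE is divided by √0.84.

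| Sizes | f | SE, no loss | Half-width: no loss / 16% loss | Power: no loss / 16% loss |
|---|---|---|---|---|
| 206 v 158 | 0.5 | 0.338 | 0.66 / 0.72 | 66% / 58% |
| 206 v 158 | 0.2 | 0.423 | 0.83 / 0.90 | 47% / 41% |
| 171 v 139 | 0.5 | 0.365 | 0.72 / 0.78 | 59% / 52% |
| 171 v 139 | 0.2 | 0.457 | 0.90 / 0.98 | 42% / 36% |

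The estimate would be informative about a large difference between groups and weak on anything smaller.

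**6. Would a rule based on excluding 0.8 work?**

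If the true difference is zero, the chance that the 95% interval lies inside ±0.8 is 2Φ(0.8/SE − 1.96) − 1. With 206 v 158, f = 0.5 and no loss it is 2Φ(0.40) − 1 = 31%. With 171 v 139, f = 0.5 and 16% loss (SE 0.399) it is about 4%. It is zero whenever the half-width exceeds 0.8.

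**The case against.** **A narrower reading of H1.** The aim itself speaks of a mixed-race population, and the race clause could mean only that enrolment was not restricted by race. The overall coefficient would then suffice. This reading is possible, but the background names effectiveness across groups as unknown, and the clause adds something the aim does not say. If the narrow meaning is intended, rewording H1 settles the matter.

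**The trial is too small for an interaction.** This stands, as step 5 shows. It argues for intervals and a limited claim. It does not justify leaving the clause unexamined.

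**The sizes could be larger and the SD smaller.** H1 refers to the mentoring arms in the plural, and U.4.1 allows usual care from both stages to be combined. Pooling gives 171 + 72 = 243 v 139 + 56 = 195, or 206 + 72 = 278 v 158 + 56 = 214. The half-width is then about 0.57 to 0.75 and power about 55 to 78% with no loss. The U.4.2 paragraph is headed as stage 1, so pooling is not the evident plan. Baseline adjustment might also narrow the intervals, but the documents do not say whether 1.6 is the SD of change or of level. Neither point supplies the missing analysis.

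**Stronger readings.** A reader might infer that the trial cannot support H1's race clause at all. The documents do not show that: baseline demographics are collected and race is a listed record item, so the effects can be estimated. The gap lies in the plan. A reader might also take effectiveness across groups to be the only new question in this aim. The background also lists persistence as unknown, and H1 covers it at 12 and 18 months.

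**Conclusion.** The concern holds as a gap between H1 and its planned analysis. Followed as written, U.4.2 can establish an average benefit in a mixed-race sample but does not test the race and ethnicity clause. In the 70/30 illustration the overall test would succeed about 80 to 87% of the time although the clause is false.

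A treatment-by-race estimate at stage 1 sizes would have a 95% half-width of about 0.66 to 0.90 units with no loss (0.72 to 0.98 with 16% loss). Power for a 0.8 difference would be about 42 to 66% (36 to 58% with loss). These figures rest on SD 1.6, no gain from baseline adjustment, and an assumed minority share of 20 to 50%, which the documents do not give.

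It might seem natural to permit the full H1 claim when the interval excludes a 0.8 difference. That should not be adopted. In the stage 1 scenarios the rule would be met at most 31% of the time even with identical effects. It would also allow, for example, 0.8 in one group and about 0.1 in the other. The primary overall test is unaffected by any of this.

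**What to change.** In U.4.2, prespecify a secondary analysis of 6-month HbA1c that adds a treatment-by-race/ethnicity term to the stage 1 model. Use African American v other as the main split, because that is where the prior evidence lies. Show other groups and ethnicity descriptively where numbers allow, since the two-way split alone does not cover all groups. Report the effect in each group and the difference, each with a 95% interval.

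State that a non-significant interaction will not be read as equal benefit, and set no equivalence-type rule on 0.8. Word the H1 conclusion as an average effect in a mixed-race population, with the race-specific estimates alongside. Confirm that the baseline demographics record both race and ethnicity, since Table 1 names neither.

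The cost is one secondary model term and a sentence on H1, with no extra patients or visits if both items are already recorded. The downside is wide intervals and a more cautious conclusion.
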